### **3.4. Attrition and Missing Outcome Data**

As described in section 1.4 some mother-babies will be matched to a childbirth-related Medicaid claim or discharge record but unmatched to a birth certificate record or fetal death vital record. We will conduct a sensitivity analysis that will include these study participants, in addition to the main sample following procedures defined in section 1.6.1. For mother-babies without a birth certificate or fetal death record, we will use hospital discharge data as the date of birth or fetal death.

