#### **1.4. Attrition and Missing Outcome Data**

For the purposes of tracking our sample, we will separately describe the share of mother-baby dyads who fall in three distinct categories where we may observe an index pregnancy, but no index birth or fetal death as follows:

1. *Probable loss of pregnancy*, which is defined as the absence of a matched birth certificate for the index birth and either (a) a matched birth certificate for a subsequent pregnancy where the birth record indicates the mother has had 0 previous live births or (b) the presence of a matched Medicaid claim or hospital discharge record containing a diagnosis or procedure code indicating a probable pregnancy loss during the index pregnancy. Below are the validated ICD-10 diagnosis codes that we use to identify probable pregnancy losses (Table 1.7).

Table 1.7. Probable pregnancy loss diagnosis codes

ICD-10-CM Code	Code Description
O02.0-O03.9	Spontaneous abortion
O00	Ectopic pregnancy
O01	Molar pregnancy

2. *Mother-baby linking error* is defined as the absence of a matched birth certificate for the index birth despite a matched record for the index birth in either Medicaid claims or hospital discharge records. The matched record in Medicaid claims or hospital discharge data must have an admission date within 120 days of the estimated due date reported on the baseline survey and an ICD-10 diagnosis code indicating a live birth according to ICD-9 claims identified by Kuklina et al. (2008) and widely used in claims-based research on birth outcomes.

3. *Unmatched pregnancy outcome* which is defined as the absence of an administrative record for a birth or pregnancy loss episode for the index pregnancy in vital records, Medicaid claims, and hospital discharge data. Some of these "unmatched" cases may eventually become probable pregnancy loss if mothers later match to a birth certificate reporting a first-time birth.

We will report rates of missingness of outcome data for each category listed across the full sample and by treatment arm in order to characterize sample attrition and identify differential attrition across treatment arms in each of these categories.

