#### **1.5.1 Calculating Adverse Birth Outcomes Without Vital Records Data**

In this section, we define the calculation of the adverse birth outcome in instances where there is a matched record for the index birth or fetal death in hospital discharge record or Medicaid claims, but not in vital records.

We identify births in hospital discharge records and Medicaid claims using the ICD-10 diagnosis code definition of live birth in Kuklina et al. (2008) and listed in Table 1.8. We will use the ICD-10 diagnosis code Z3A to calculate gestational age. In cases where an ICD-10 code for gestational age is absent from the hospital or Medicaid claim record, we will calculate gestational age at birth using the admission date on the record and the expected due date as given in the baseline survey. The preterm birth component of the adverse birth outcome will be coded as 1 if the gestational age on the health record is less than 37 weeks, or, if the record contains a diagnosis code P07.30-P07.39. The low-birth weight component will be coded as 1 if the record contains a diagnosis code P07.0-P07.18. The SGA component will be coded as 1 if the record contains a diagnosis code of P051. Fetal deaths will be identified with the codes in Table 1.9 when accompanied by an ICD-10 diagnosis code Z3A for gestational age of at least 20 weeks.

---

Table 1.8. Codes to Identify Live Births

ICD-10 Code(s)	Code Description	Exclusion Code
080, 082	Encounter for delivery	No
Z37	Outcome of delivery	No
10D00Z0, 10D00Z1, 10D00Z2	Extraction of products of conception	No
10D07Z3, 10D07Z4, 10D07Z5, 10D07Z6, 10D07Z7, 10D07Z8	Forceps/Vacuum/Breach	No
OW8NXZZ	Episiotomy	No
10A07ZZ, 10A00ZZ, 10A03ZZ, 10A04ZZ, 10A07ZX, 10A07ZW, 10A07Z6, 10A08ZZ	Abortion of products of conception	Yes
0019	Hydatidiform mole, unspecified	Yes
0048	Shock following (induced) termination of pregnancy	Yes
002	Missed abortion	Yes
000	Tubal pregnancy without intrauterine pregnancy	Yes
003	complete or unspecified spontaneous abortion without complication	Yes
008	Complications following ectopic and molar pregnancy	Yes

Table 1.9. Fetal Death Codes

ICD-10 Code(s)	Code Description	Exclusion Code
Z37.1	Single stillbirth	No
Z37.4	Twins, both stillborn	No
Z37.7	Other multiple births, all stillborn	No
P95	Stillbirth on child claims (occasionally appears on Mother claims)	No
036.4	Maternal care for intrauterine death	No

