##### **3.2.1. Construction of birth spacing outcomes**

Data will be obtained from vital statistics birth records. In the case of multiples, birth spacing will be measured as the time between the date of birth of the last child from the index pregnancy to the date of birth of the first child from the subsequent pregnancy. There may be cases where the subsequent birth is implausibly close to the index birth. Births that occur less than or equal to 90 days from the index birth will be assumed to be multiple gestation based on guidelines provided by the National Center for Health Statistics. Subsequent births that occur between 90 days and 21 weeks (147 days) after the index birth will be considered outliers and will be dropped from the analysis. We define birth outcomes of interest in Table 3.1.

Table 3.1. Birth spacing outcomes

Birth spacing outcomes	Follow-up
Inter-birth interval of < 21 months (primary outcome)	21 months
Inter-birth interval of < 24 months	24 months
Inter-birth interval of < 15 months	15 months

Inter-birth interval (continuous)	60 months
-----------------------------------	-----------

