### 3.3. Timing of Study analyses

We will complete this analysis once all study births have occurred, and at least 24 months have elapsed following the last study birth. We will add additional lags to account for the time it takes for administrative records to be complete, sent to the study team, and matched to existing analytic files. Based on the estimated delivery date collected in the baseline survey, the latest expected study delivery date is November 7, 2020. As we define births within a 120-day window of the estimated gestational age as a study index birth, the latest possible date when a study index birth could occur is March 7, 2020. We will allow for twenty-four months of follow-

up from the time of the final possible study index birth (March 7, 2022), six additional months for the study outcomes to be fully incorporated into South Carolina administrative data (September 7, 2023), and an additional three-month buffer for the administrative data to be matched with the study dataset (December 7, 2023). Therefore, we anticipate that analyses of these outcomes will begin in December 2023.

This study includes four birth spacing outcomes. The first three are birth interval indicators defined as having no subsequent live birth observed within 21 (primary outcome), 15 and 24 months (secondary outcomes) of the index birth. The fourth is a continuous outcome defined as the number of months before any subsequent birth within 60 months of the index birth. The analysis for this outcome will include only women who went on to have another birth within 60 months of their index birth. The first three of the birth spacing outcomes described in Table 3.1 will be reported in the main manuscript for the maternal life course objective. The continuous birth interval outcome will be included in a later manuscript which will include longer-term maternal outcomes.

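### The birth-spacing sensitivity analysis in SAP 3.4 adds women with no vital record but names only vital records as the source for their next birth, which weakens it as a check on linkage bias

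*SAP*

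**What the plan says.** SAP Addendum 3, 3.2.1, gives one source for birth spacing: "Data will be obtained from vital statistics birth records". Section 3.3 defines the three interval indicators as "having no subsequent live birth observed within 21 (primary outcome), 15 and 24 months (secondary outcomes) of the index birth". A woman for whom no next birth is found is therefore counted with those who had none, rather than as missing.

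Section 3.4 deals with women who have a childbirth record in claims or discharge data but no birth certificate or fetal death record: "We will conduct a sensitivity analysis that will include these study participants, in addition to the main sample following procedures defined in section 1.6.1". It then adds: "For mother-babies without a birth certificate or fetal death record, we will use hospital discharge data as the date of birth or fetal death".

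The SAP has no section 1.6.1; its section 1.6 is on subgroups. The likely target is 1.5.1, whose scope is "a matched record for the index birth or fetal death in hospital discharge record or Medicaid claims, but not in vital records". That section rebuilds the adverse birth outcome from diagnosis codes and gives no rule for a later birth.

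Section 1.4 defines a mother-baby linking error as "absence of a matched birth certificate for the index birth despite a matched record for the index birth", and commits to reporting each category of missing outcome data by treatment arm.

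**The concern.** The added women are in the analysis because a match to vital records failed for the index birth. If whatever caused that also affects the next birth, for example poor identifiers given at enrolment (listed in A.2 as a reason for failed matching), the next birth is missed in the same source. It is then scored as a good outcome.

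Addendum 1 handles the parallel problem differently. Its robustness check extends the sample and also rebuilds the outcome from claims and discharge codes. Addendum 3 takes over the extended sample but not an alternative source for the outcome.

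This is the only check that Addendum 3 plans of birth spacing against linkage failure. Section 3.5 is about contraception and Medicaid coverage, and the re-analysis on updated records in A.2 is optional. Agreement between the main and extended analyses could be read as reassurance that the data cannot fully give.

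**Working it through.** **Inputs from Protocol 5.2.** Risk of a short interval without NFP 0.14 (SD 0.34); expected effect −18%; 4,000 versus 2,000 women; 95% take-up; at most 5% of controls with an equivalent programme; stated power roughly 70%. The two-sided 0.05 level is in Protocol 5.1.

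**Plan's own figure.** Planned effect: 0.18 × 0.14 = 0.0252, or 2.52 points. With net exposure 0.95 − 0.05 = 0.90 it is 0.0227. SE = 0.34 × √(1/2,000 + 1/4,000) = 0.00931, so z = 0.0227/0.00931 = 2.44 and power = Φ(2.44 − 1.96) ≈ 68%. A two-proportion calculation (0.140 versus 0.117) gives 70.3%. The stated figure reproduces.

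**Assumed inputs.** u = added women as a share of the extended sample, range 1% to 10% (SAP 1.5 calls the group small and gives no figure). f = share of their next births also missed in vital records, range 0 to 1.

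**1. How many added women are wrongly scored?** Share = 0.14 × f: 3.5% at f = 0.25, 7% at f = 0.5, 14% at f = 1. The other 86% have no short interval even with perfect linkage, if their risk is 14%.

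**2. Equal u in both arms.** Observed rate = p(1 − u) + u·p·(1 − f) = p(1 − u·f), so the treatment difference shrinks by u × f.

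| u | f = 0.5 | f = 1 |
|---|---|---|
| 1% | 0.5% | 1% |
| 3% | 1.5% | 3% |
| 5% | 2.5% | 5% |
| 10% | 5% | 10% |

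**3. Unequal u, no true effect.** Spurious difference (treatment minus control) = 0.14 × f × (u in control − u in treatment).
- 1-point gap, f = 1: 0.14 points, or 0.0014/0.0252 = 6% of the planned effect.
- 2-point gap, f = 1: 0.28 points, or 0.0028/0.0252 = 11%.
- 2-point gap, f = 0.5: 0.14 points, 6%.

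For scale, with the 3,295 and 1,637 index births in Addendum 4, Table 3, the SE of the difference at 14% risk is √(0.14 × 0.86 × (1/3,295 + 1/1,637)) = 1.05 points. So 0.28 points is 0.27 SE.

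**4. Can the check hide or reverse a bias?** Let the added women's true risk be r, and let the linked women's be 0.14. Within one arm the extended analysis shows 0.14(1 − u) + u·r·(1 − f). For r above 0.14 it moves the right way only if r(1 − f) > 0.14, that is f < 1 − 0.14/r. With u = 5% and r = 0.28 (assumed), the true rate is 0.133 + 0.014 = 14.7%, and the check shows:
- f = 0: 14.7%, correct.
- f = 0.5: 14.0%, identical to the main sample, so the bias is hidden.
- f = 1: 13.3%, the wrong direction.

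With r = 0.20 the turning point is f = 1 − 0.14/0.20 = 0.30. These are rates in one arm; the treatment contrast is misread to the extent that the arms differ in u, r or f.

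**The case against.** A reader might infer that most added women are scored event-free by default, or that the check cannot test linkage bias at all. The documents support neither. At the planned 14% risk, 86% of these women are correctly event-free, and at most 14% can be misclassified. The check is void only as f nears 1. Linking error is defined on the index birth, and nothing says that it persists. These women did match claims or discharge data, so their identifiers worked in at least one state source. A.2 expects matches to change as records update. Section 1.4 also foresees, for a woman with no index certificate, "a matched birth certificate for a subsequent pregnancy where the birth record indicates the mother has had 0 previous live births". That text describes probable pregnancy loss, not the linking-error group, but it shows that a later match is possible.

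It can also be said that the SAP never states a vital-records-only rule for these women. This is right: with a faulty cross-reference, it is the best reading and not an explicit instruction.

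Finally, the arm imbalances above are assumed, the distortion is small against the standard error, and 1.4 would show an imbalance in linking errors by arm. All of that stands. Reporting u by arm does not, however, reveal f, which decides whether the extended analysis is informative.

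**Conclusion.** The point holds in a limited form. The sensitivity analysis replaces the index date but names no second source for the event, so each next birth that fails to link becomes a non-event. The check is weakened, and can conceal or reverse a bias, in proportion to how far linkage failure persists.

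The size is modest: attenuation of u × f with equal shares, and 0.28 points (11% of 2.52) with a 2-point imbalance and every next birth missed. Both u and f are assumptions because the documents give neither. The main birth-spacing analysis uses the same rule that an unobserved birth counts as none, but this point is confined to the sensitivity analysis. It is a cheap improvement to a secondary check, not a threat to the primary result.

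**What to change.** In SAP 3.4:

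1. Correct the cross-reference to 1.5.1 and state how the next birth is found.
2. For this sensitivity analysis, in both arms, identify the subsequent live birth from vital records or all-payer hospital discharge records. Use the delivery codes of Table 1.8 with its exclusions, and remove the stillbirth codes of Table 1.9. Z37 in Table 1.8 otherwise takes in Z37.1, Z37.4 and Z37.7, while the outcome is a live birth. Apply the existing 90-day and 147-day rules so that the index delivery is not counted again.
3. Show births seen only in Medicaid claims separately. Section 3.5 warns that NFP may affect coverage after 60 days, so detection in claims could differ by arm.
4. Report the extended sample alone first, then with the added outcome source, so that the two changes can be told apart.
5. Report by arm how many added women match any later vital record. This gives a direct indication of whether linkage failure persists.

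Addendum 4 lists family planning among papers published or forthcoming. If the check has already been run, the sponsor should state how the next birth was found and add the revised version.

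The cost is wording and modest programming, since discharge data are already among the study's sources. Some dates will be slightly approximate.

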### **3.5. Endogeneity of Outcome Data and Sensitivity Analyses**

Because outcomes related to contraceptive uptake will rely primarily on Medicaid claims data, we cannot observe contraception use in outpatient settings among women who are not enrolled in Medicaid. As a non-expansion state, all women with Medicaid pregnancy coverage in South Carolina, except undocumented and recent immigrants, retain Medicaid coverage for at least 60 days following childbirth. Women who qualify for other payment categories (e.g. foster-care, disability), may retain coverage past 60 days. Because NFP may affect maintenance of Medicaid coverage past 60 days postpartum, including maintenance of enrollment in Medicaid Family Planning coverage, we may not be able to observe treatment and control group mothers in the Medicaid claims data at equal rates.

To determine whether continuous Medicaid coverage differs between treatment groups, we will first compare continuous Medicaid coverage of any type (coverage through the low-income families, qualified disabled workers, pregnancy and family planning eligibility pathways), and

family planning Medicaid coverage specifically, between treatment and control groups at the three contraception outcome time points (6 weeks, 12 and 24 months). Continuous coverage will be measured using Medicaid enrollment data and will be defined as enrollment during all months, starting with the month of childbirth through 6 weeks, 12 and 24 months postpartum. It is also possible that while average Medicaid enrollment will not differ between the two groups, the type of women retaining coverage will be affected by NFP. Therefore, using a joint F-test, we will also test whether there are differences in the characteristics of participants between control and treatment groups enrolled in Medicaid during the three-outcome time points (60 days, 12 months, 24 months).

When conducting the study analysis, we will divide outcomes between those that we observe within 60 days after childbirth (when nearly all women retain Medicaid), and those measured after 60 days postpartum. Our main analysis will include the full sample of women regardless of postpartum Medicaid coverage after 60 days, but we will also examine the outcomes in the subgroup of women who retained coverage for 24 months postpartum. If we find evidence that NFP affected average Medicaid enrollment or the type of woman enrolling in Medicaid, we will place more emphasis on the 6-week contraception outcomes when Medicaid coverage loss is minimal and more likely to be balanced between groups. Alternatively, if we find little evidence of differential coverage loss at 12 and 24 months, we will consider contraception outcomes at all three time points.

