In our clinical trials registry, we defined a measure of mental health treatment follow-up care as: a second antidepressant prescription or outpatient mental health visit within 120 days of the initial treatment ("acute phase"). However, as noted above, differential Medicaid coverage rates between the treatment arms after 60 days postpartum may preclude us from measuring the treatment effect for this outcome reliably. For example, if treatment group members are more likely to be enrolled in Medicaid after 60 days postpartum than control group members, observed differences in mental health treatment patterns between the treatment and control groups could be due to group differences in the composition of who remains on Medicaid.

To assess whether attrition from full-coverage Medicaid plans affects the comparability of the treatment and control groups, we will assess overall attrition and differences in attrition between the treatment and control groups at the following time points: 60 days (for our main outpatient mental health treatment outcomes), 6 months, 12 months and 24 months postpartum (for other potential measurement periods of interest). We do not consider enrollment in partial-coverage Medicaid plans (such as Family Planning) since these plans cover mental health screenings, but do not reimburse for medications or psychotherapy. Specifically, we will compare partial and continuous enrollment rates in full coverage plans between treatment and control groups at each time point. Continuous coverage will be measured using Medicaid enrollment data and will be defined as enrollment during all months, starting with the month of childbirth through 60 days, 6 months, 12 months and 24 months postpartum. It's possible that while average Medicaid enrollment will not differ between the two groups, the type of women retaining coverage could be affected by NFP. Therefore, we will also test whether the treatment and control group members who remain in the analytic sample at each time point are similar on important baseline characteristics using a joint F-test.

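### SAP 3.5 compares the arms only on unbroken Medicaid enrolment, which can show no difference while the arms differ in the months over which contraception after 60 days can be observed

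*SAP*

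**What the plan says.** SAP Addendum 3, section 3.2.2, takes the contraception outcomes mainly from Medicaid claims, with hospital discharge data added for inpatient provision. Section 3.5 states the consequence: "we cannot observe contraception use in outpatient settings among women who are not enrolled in Medicaid". It adds that women with pregnancy coverage, apart from undocumented and recent immigrants, "retain Medicaid coverage for at least 60 days following childbirth", and that NFP may affect coverage after that point, Family Planning coverage included.

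Two checks follow in 3.5.

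- **Coverage.** The arms are compared on continuous coverage of any type, pooling "coverage through the low-income families, qualified disabled workers, pregnancy and family planning eligibility pathways", and on "family planning Medicaid coverage specifically, between treatment and control groups at the three contraception outcome time points". Continuous coverage is "defined as enrollment during all months, starting with the month of childbirth through 6 weeks, 12 and 24 months postpartum". No other coverage measure is defined.
- **Composition.** A joint F-test compares the characteristics of enrolled women between arms.

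The last paragraph of 3.5 keeps the full sample in the main analysis whatever coverage a woman has after 60 days, and also examines women who kept coverage for 24 months. If NFP affected average enrolment or the type of woman enrolled, emphasis moves to the 6-week outcomes. Otherwise, "if we find little evidence of differential coverage loss at 12 and 24 months, we will consider contraception outcomes at all three time points".

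For maternal mental health outcomes, Addendum 1 sets a broader comparison: "we will compare partial and continuous enrollment rates in full coverage plans between treatment and control groups at each time point".

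**The concern.** In the main analysis a woman is recorded as having no outpatient contraceptive service in any month when Medicaid does not cover her. The chance of observing a service therefore rises with the number of covered months. The planned comparison does not count months. It asks whether a woman was covered in every month from childbirth. A woman who misses one month when pregnancy coverage ends and then returns gets the same score as a woman who leaves for good at 60 days.

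Suppose NFP leads more women to return after a gap. Covered months would then differ between arms without any change in the continuous rate. The emphasis rule could give the later outcomes equal standing, and a difference in observation could be read as an effect on contraceptive use.

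The family-planning comparison raises a further question. If the same definition governs it, a woman must be on that pathway from the month of childbirth, when most women hold pregnancy coverage.

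**Working it through.** The documents state no coverage rate, threshold or power for this check, so there is no planned figure to reproduce. Two questions can be worked: how far covered months can differ at equal continuous rates, and whether such a gap could matter for an outcome.

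**Step 1. Limits at equal continuous rates.** Count the birth month as month 0, which gives 13 months to month 12 and 25 to month 24. Let c be the continuous rate, the same in both arms (assumed 10% to 50%). Take months 0 to 2 as covered for all, following the 60-day statement in 3.5. A woman without continuous coverage then has between 3 months and all but one.

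Largest arm gap in mean months = (1 − c) × (total − 1 − 3).

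| c | 12 months: (1 − c) × 9 | 24 months: (1 − c) × 21 |
|---|---|---|
| 10% | 8.1 | 18.9 |
| 20% | 7.2 | 16.8 |
| 30% | 6.3 | 14.7 |
| 50% | 4.5 | 10.5 |

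**Step 2. What each comparison detects.** Assume that, of women without continuous coverage, 20% in control and 40% under NFP return after a one-month gap, and the rest stop after month 2. Use 3,295 and 1,637 women, the index-birth denominators in SAP Addendum 4, Table 3 (the Addendum 3 sample also includes fetal deaths). Test at two-sided 0.05, which Protocol 5.1 states for impact estimates; none is stated for this check.

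At c = 20%, mean months of 13 are:

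- control: 0.2 × 13 + 0.8 × (0.2 × 12 + 0.8 × 3) = 6.44
- NFP: 0.2 × 13 + 0.8 × (0.4 × 12 + 0.6 × 3) = 7.88

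The gap is 1.44 months. At 24 months the same steps give 10.76 and 14.12, a gap of 3.36. For c from 10% to 50% the gap runs from 1.6 down to 0.9 months at 12 months, and from 3.8 down to 2.1 at 24 months. In 4,000 simulations per value of c, using the 24-month window, comparing continuous rates rejected 4.7% to 5.3% of the time, which is only its type I error. Comparing mean months rejected in practically every run.

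**Step 3. Effect on a 12-month outcome with no true difference.** Assume a share h0 has a claim by month 2, then a 5% monthly chance while covered, the same in both arms. The false difference at 12 months is

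(1 − c) × (0.40 − 0.20) × (1 − h0) × (1 − 0.95^9), with 1 − 0.95^9 = 0.370.

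The standard error is √[p(1 − p)(1/3295 + 1/1637)] = 0.0302 × √[p(1 − p)]. At c = 20%:

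| h0 | Control | NFP | False difference | In SE |
|---|---|---|---|---|
| 30% | 39.8% | 43.9% | 4.1 points | 2.8 |
| 60% | 65.6% | 67.9% | 2.4 points | 1.7 |

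With 20% versus 30% returning, both differences halve, to 2.1 and 1.2 points (1.4 and 0.8 SE). The result therefore turns on inputs that the documents do not supply. No 24-month rate is worked, because the 24-month contraception outcomes in Table 3.2 are times to first service.

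**Step 4. Family-planning comparison.** Section 3.5 lists pregnancy and family planning as separate pathways and gives one definition of continuous coverage. If that definition applies here, and pregnancy and family-planning enrolment are not recorded in the same month, a woman on pregnancy coverage in the birth month scores zero at all three time points whatever happens later.

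**The case against.** The strongest reply is that 3.5 does not rest on the continuous rate alone.

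- **Second trigger.** The rule also responds to the joint F-test. That stands, and the test would catch some cases. It compares who is enrolled, not for how long, so it would miss a difference in months unrelated to baseline characteristics.
- **Retained subgroup.** Women covered for 24 months have equal observation time. In the artefact-only setting of step 3 their expected difference is zero, and a null there beside a positive main result would be a warning. This is useful, but the subgroup is smaller and is selected on a post-randomisation variable that NFP may affect.
- **Seamless transfers.** Any-type coverage pools the pathways, so a move from pregnancy to Family Planning coverage without a gap is counted as continuous. That stands. The weakness is limited to coverage with gaps or of differing length.
- **Continuous coverage would probably move too.** If NFP raised it by 5 points, the planned comparison would have about 91% power or more at starting rates of 10% to 50%. For 3 points, power is 51% to 87%. The weakness bites when the difference lies mainly among women with gaps.
- **Emphasis only.** The rule shifts emphasis and sets no numerical gate, and its reference to average enrolment could be read more broadly. That is fair, but no other measure is defined.

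A reader might infer that the family-planning comparison is near zero by construction. The documents do not establish this. The sentence can be read as enrolment at each time point, and nothing says that the two kinds of enrolment are never recorded together. A reader might also infer that the later outcomes are biased by several points; the rates needed to show that are absent. Nor does Addendum 1 use covered months: it adds partial enrolment, without defining it.

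**Conclusion.** The point holds as a gap in the check. Unbroken enrolment is the only coverage quantity that 3.5 defines, while observation of the outcomes depends on months covered, and the first can be equal between arms when the second is not. The F-test and the retained subgroup reduce the risk of a wrong reading without removing it.

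The size of any bias is unknown. The limits in step 1 rest on assumed continuous rates and three guaranteed months. The false differences of 1.2 to 4.1 points in step 3 rest on assumed return rates and claim rates, and only one of the four cases exceeds 1.96 standard errors. The family-planning part is conditional on the two readings in step 4, and the main point does not depend on it.

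Reach is limited to contraception outcomes measured after 60 days. The primary outcome, an inter-birth interval under 21 months, comes from vital records (section 3.2.1) and is not affected.

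**What to change.** In SAP 3.5:

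1. Beside the continuous rate, report by arm, with confidence intervals, any enrolment and mean months enrolled within 12 and 24 months postpartum, counting coverage that pays for contraception. This follows the spirit of the partial-and-continuous comparison in Addendum 1.
2. Measure family-planning enrolment from the end of the 60-day pregnancy coverage, and say which definition governs that comparison.
3. State that average enrolment and differential coverage loss, as used in the emphasis rule, include these measures.

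The enrolment file is already used for the planned check, so the cost is some wording, a few lines of code and one or two more rows in the coverage table. Addendum 4 lists family-planning results among manuscripts published or forthcoming. If that analysis has been run, report the added measures as a supplementary check and label them as added later.
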